## 9. SAFETY ASSESSMENT

### 9.1. Specification of Safety Parameters

All adverse events occurring during the course of the trial shall be recorded and assessed in order to evaluate the safety. They will be analyzed thoroughly, both during scheduled controls and whenever a subject notifies an abnormal incident. Exacerbations of COPD will not be considered Adverse Events because they constitute events that are to be expected within the course of the disease and their quantification is the primary objective of this trial.

Adverse events spontaneously manifested by a subject throughout the entire trial should also be recorded, always avoiding questions that might guide the subject's response.

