## 5. TRIAL DESIGN

### 5.1. Description of the Primary and Secondary Outcome

- **Primary outcome:**

- The primary efficacy outcome is a decrease in the mean number of COPD exacerbations. A clinical diagnosis of an exacerbation according to the GOLD definition will be considered; that is, an event occurring throughout the natural course of the disease, characterized by a change of acute onset, beyond the daily variability, in the patient's dyspnea, cough, and/or expectoration, which may require a change in the patient's usual medication.

- **Secondary outcomes:**

- Decrease in the rate of COPD exacerbations per study group at 12 months (end of the trial treatment) and 6 months after the trial's termination (follow-up).
- Decrease in the severity of the COPD exacerbations. The severity of the exacerbations will be measured based on the consumption of healthcare resources (i.e., visits to the Emergency Department, hospitalizations, or consultations), as follows:
  - ICU hospitalization: 4 points.
  - Standard hospitalization: 3 points.
  - Emergency Department visit: 2 points.
  - Consultation involving a change in the patient's usual treatment: 1 point.

[name]  
Traductor-Intérprete Jurado de INGLÉS  
Nº 9971

- Time elapsed between the start of the treatment and the first COPD exacerbation.
- Use of drugs (antibiotics, corticosteroids, etc). Drug consumption will be scored as follows:
  - Use of antibiotics: 1 point.
  - Use of inhaled corticosteroids: 2 points.
  - Use of systemic corticosteroids: 3 points.
  - Use of oxygen therapy: 4 points.
  - Use of mechanical ventilation: 5 points.
- Number of hospitalizations due to COPD exacerbations.
- Days of hospitalization due to COPD exacerbations.
- Number of visits to the Emergency Room.
- Number of unscheduled medical consultations due to COPD exacerbations.
- Health-related quality of life, as determined by an adapted version of the specific CAT test.
- Healthcare expenditure resulting from resource consumption during episodes of COPD exacerbations occurring during the trial period.
- Variations (change between the baseline level and months 0, 3, 6, and 12, as well as in comparison with the placebo) in the following immunological parameters in the patients participating in the immunological substudy (N = 60) and/or those of the subgroup of the induced sputum study (N = 20) (between month 0 prior to the administration of the vaccine and month 12).

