#### **5.6. Description of the Subject “Termination Criteria” and “Discontinuation Criteria” During the Entire Trial or Parts of It**

The trial shall end with the trial's database lock.

Subjects may temporarily discontinue the treatment for 7 to 14 days in any of the following cases:

- Severe or very severe COPD exacerbation.

Acute exacerbations will be graded according to the following scale:

1. Mild (home care with or without contact with the subject's doctor).
2. Moderate (requiring a visit to the Emergency Department).
3. Severe (requiring hospitalization).
4. Very severe (requiring intubation and mechanical ventilation).

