## 9.2. Methods and Schedule Used to Assess, Record, and Analyze the Safety Parameters

### Definitions:

- **Adverse Event (AE):** any untoward health occurrence in a Subject or a clinical trial subject treated with a medication and which does not necessarily have a causal relationship with the treatment. Exacerbations of COPD will not be considered Adverse Events because they constitute events that are to be expected within the course of the disease and their quantification is the primary objective of this trial.
- **Adverse Reaction (AR):** any unintended and harmful response to an investigational medicinal product, regardless of the dose administered.

- **Serious Adverse Event (SAE):**

Any adverse event that, at any dose:

- Leads to death.
- Is life-threatening for the subject (term “life-threatening” included in the definition of SAE refers to the fact that the Subject is at a risk of dying as a result of the event but not that, had the event been more intense, it could have caused the Subject's death).
- Results in the hospitalization or prolongation of an existing hospitalization.
- Causes a permanent or significant disability or incapacity.
- Results in a congenital anomaly or birth defect.
- Involves the transmission of any infectious agent (through the medicinal product).

The investigator shall rely on their own medical judgment to determine whether an Adverse Event is serious in other situations. Major medical events that, despite not posing an immediate risk of death or not resulting in death or hospitalization, may endanger the subject or require intervention to prevent one of the other outcomes listed in the above definition, should also be considered serious.

- **Suspected Unexpected Serious Adverse Reaction (SUSAR):** an adverse reaction whose nature or seriousness is not consistent with the product information (e.g., the investigator's brochure in the case of an investigational medicinal product not authorized for marketing or a summary of product characteristics in the case of an authorized medicinal product).

Adverse reactions can be classified into:

- **Local reactions**

Those appearing in the administration site. They may manifest as a mild burning, swelling, or itchy sensation in the oropharyngeal region. Gastrointestinal discomfort may develop in some cases. The onset of local reactions does not imply that the dosing schedule should be discontinued or changed. Their presence should be carefully assessed.

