### **9.3. Procedures for Recording and Reporting Adverse Events and Intercurrent Diseases, and for Submitting their Reports**

All events meeting the definition of an adverse event should be collected and recorded between the start of the first trial-related activity (after the subject's signature of the informed consent) and the end of the post-treatment follow-up period required by the protocol. Subjects will be questioned whether they noticed any adverse event during each visit to the site. All adverse events, whether observed by the investigator or reported by a subject, should be recorded in the corresponding section of the case report form and evaluated by the investigator.

The minimum information to be specified shall be the description, severity, duration, temporal sequence, and method of detection of the adverse event. The treatment administered to manage the event must also be specified.

The investigator shall immediately report all serious adverse events and/or suspected unexpected serious adverse events (SUSARs), regardless of their relation to the investigational medicinal product, by telephone ( [REDACTED] ) or fax ( [REDACTED] ), to the staff of Inmunotek's Medical Department (always within the first 24 hours of their onset). The initial and follow-up reports shall identify the trial subjects by a unique identification code assigned to each one of them.

[name]  
Traductor-Intérprete Jurado de INGLÉS  
Nº 9971

The regulations in force will be followed when issuing the safety information notification to the Health Authorities, the Research Ethics Committees, and the investigators.

If a suspected unexpected serious adverse reaction occurs within the context of a double-blind clinical trial, the treatment code of the particular subject must be disclosed for reporting purposes. Whenever possible, blinding should be maintained for the investigator and the persons responsible for the analysis and interpretation of the results, as well as for drafting the study conclusions.

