6.1.2. Secondary outcomes

- ★ Decrease in the rate of COPD exacerbations per study group at 12 months (end of the trial treatment) and 6 months after the trial's termination (follow-up).
- ★ Decrease in the severity of the COPD exacerbations. The severity of the exacerbations will be measured based on the consumption of healthcare resources (i.e., visits to the Emergency Department, hospitalizations, or consultations), as follows:
 - ICU hospitalization: 4 points.
 - Standard hospitalization: 3 points.
 - Emergency Department visit: 2 points
 - Consultation involving a change in the patient's usual treatment: 1 point.
- ★ Time elapsed between the start of the treatment and the first COPD exacerbation
- ★ Use of drugs (antibiotics, corticosteroids, etc). Drug consumption will be scored as follows:
 - Use of antibiotics: 1 point.
 - Use of inhaled corticosteroids: 2 points.
 - Use of systemic corticosteroids: 3 points.
 - Use of oxygen therapy: 4 points.
 - Use of mechanical ventilation: 5 points.
- ★ Number of hospitalizations due to COPD exacerbations.
- ★ Days of hospitalization due to COPD exacerbations.
- ★ Number of visits to the Emergency Room.
- ★ Number of unscheduled medical consultations due to COPD exacerbations.
- ★ Health-related quality of life, as determined by an adapted version of the specific CAT test.
- ★ Healthcare expenditure resulting from resource consumption during episodes of COPD exacerbations occurring during the trial period.
- ★ Variations (change between the baseline level and months 0, 3, 6, and 12, as well as in comparison with the placebo) in the following immunological parameters in the patients participating in the immunological substudy (N = 60) and/or those of the subgroup of the induced sputum study (N = 20) (between month 0 prior to the administration of the vaccine and month 12).

In the case of patients participating in the IMMUNOLOGICAL SUBSTUDY (n = 60), changes in the below parameters will also be assessed during the randomization visit (visit 1) and the visits corresponding to months 3, 6, and 12:

- The specific humoral response [REDACTED]
- The in vitro proliferative response of specific T cells [REDACTED]

In a subgroup of patients (n = 20) selected from the group of patients participating in the immunological substudy (n = 60), the following parameters will also be evaluated in samples of induced sputum at month 0 (visit 1) and month 12:

- ★ IgA response to Bactek antigens assessed using ELISA technique.

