7.1.6. Interim Analysis

There is no interim analysis planned.

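### Exacerbations are excluded from adverse events with no exception for fatal or life-threatening cases, and no planned output by arm identifies a death from an exacerbation

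*Protocol*

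**What the plan says.** Protocol 9.1 sets the rule: "Exacerbations of COPD will not be considered Adverse Events because they constitute events that are to be expected". The definitions in Protocol 9.2 repeat it under the adverse event entry: "Exacerbations of COPD will not be considered Adverse Events because they constitute events that are to be expected within the course of the disease". Both places add that counting exacerbations is the trial's primary purpose. Neither qualifies the rule by outcome, seriousness or suspected cause.

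The SAE definition in the same section opens "Any adverse event that, at any dose" and then lists death, threat to life, hospitalisation and further criteria. Protocol 9.3 requires SAEs and SUSARs to reach the sponsor within 24 hours. Protocol 9.4.2 follows SAEs to a final outcome, which may be death. SAP 7.5 summarises adverse events by severity, relationship, outcome and seriousness.

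On the efficacy side, the severity score in Protocol 5.1 and SAP 6.1.2 has as its top category "ICU hospitalization: 4 points". The drug and support score in the same sections ends at "Use of mechanical ventilation: 5 points".

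**The concern.** The protocol's own background (3.2) says that severe exacerbations carry substantial mortality. Protocol 6.1 admits patients with at least three moderate exacerbations in the past year, or two of which one led to hospital admission. A death from an exacerbation is therefore a foreseeable event in this trial, and its balance between arms is something a reader of the safety results would expect to find.

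If exacerbations leave the adverse event system, that information has to come from elsewhere in the plan. If it does not, there is a second problem. Deaths from other causes would still enter SAP 7.5 as adverse events with a fatal outcome. The table would then show part of the mortality and could be read as showing all of it.

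**Working it through.** The plan states no figure to reproduce. The check follows one fatal exacerbation through each route by which the documents could record or display it.

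1. **Adverse event tables** (Protocol 9.1 and 9.2; SAP 7.5). The event is excluded by definition, so its outcome and seriousness are not tabulated.
2. **SAE report and follow-up** (Protocol 9.2, 9.3, 9.4.2). An SAE must first be an adverse event. This event is not one, so neither the 24-hour report nor follow-up to death applies.
3. **Adverse reaction and SUSAR** (Protocol 9.2, 9.3). An adverse reaction is defined as a harmful, unintended response to the product, without reference to the adverse event definition, and a SUSAR is a type of adverse reaction. If the investigator attributes the exacerbation to the product, this route is arguably open. It yields an individual report, not a planned comparison.
4. **Severity score** (Protocol 5.1; SAP 6.1.2). It runs from 1 point for a consultation that changes treatment to 4 for ICU. It records resource use, so an ICU admission that ends in death scores the same as one that is survived.
5. **Drug and support score** (same sections). It runs from 1 to 5 and stops at mechanical ventilation. Death has no category.
6. **Exacerbation grade** (Protocol 5.6). The highest of four grades is intubation with ventilation. There is no fatal grade.
7. **Exacerbation count and time to first exacerbation** (SAP 7.4.1, 7.4.2). The event counts as an exacerbation, with nothing to mark it as fatal.
8. **Disposition table** (SAP 7.2). By arm it shows the analysis sets, the number enrolled and the number withdrawn. It gives no cause.
9. **CRF and listings** (Protocol 6.3.1, 6.3.2; SAP 7.1). Withdrawal causes and dates are to be recorded, and listings include all available data, so the fact may exist there. Death is not a named cause in 6.3.1. Table 1 schedules the termination cause at visits 1 to 4 (months 0 to 12) and not at months 15 and 18. No summary of causes by arm is specified.
10. **Outcome lists** (Protocol 4.1, 5.1, 8.1; SAP 6.1.1 to 6.1.3). Mortality is not a primary, secondary or safety outcome.

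Planned outputs by arm that identify an exacerbation death as a death: 0.

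A life-threatening exacerbation that is survived follows a different path. It misses routes 1 and 2, but routes 4 and 5 pick it up as ICU care or ventilation. SAP 7.4.1 compares severity between arms, and SAP 7.4.2 analyses the number and duration of admissions.

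**The case against.** The strongest reply is that the exemption is deliberate and reasoned. Exacerbations are expected in this disease and are the primary endpoint, and leaving an endpoint out of routine adverse event reporting is not an error. That stands. The gap is only the missing exception for the gravest cases, with no mortality table in its place.

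Four stronger readings are tempting, and the documents do not support them.

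- A reader might infer that no exacerbation can ever be a SUSAR. The exclusion is attached to the adverse event definition, while adverse reaction is defined separately. At most the wording is ambiguous.
- A reader might infer that severe exacerbations disappear from the comparison of arms. ICU and hospitalised exacerbations are compared as efficacy outcomes, so a further table of them would largely duplicate planned output.
- A reader might take "There is no interim analysis planned" to mean that nobody oversees safety. That sentence concerns efficacy looks. The available text describes no safety committee, but administrative pages are missing from it, so this is weak evidence.
- A reader might want a number of deaths hidden by the rule. The documents give no mortality or admission rate. The planned 180 subjects followed for 18 months also cannot be treated as full exposure when 20-25% dropout is assumed. No count is offered here.

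It is also fair to say that a rise in exacerbations on active treatment would show in the primary analysis. That does not replace a death count, because death ends a subject's exacerbation count.

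Finally, the change to reporting may come too late. Protocol 5.5 ends recruitment on 31 March 2018, and 18 months later is the end of September 2019. The SAP cites 2021 guidance and 2022 software. This limits the protocol part of the remedy, but not the tables, which the SAP can still specify before database lock.

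**Conclusion.** The concern holds in a limited form. As written, fatal and life-threatening exacerbations are outside SAE reporting and the SAP 7.5 tables. For life-threatening cases that are survived, the efficacy analyses supply most of what is missing. For deaths they do not: an analysis that followed the plan exactly would contain no output by arm showing how many patients died of an exacerbation.

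This rests on reading the definitions literally and on the outputs that the SAP names. It does not claim that deaths would go unrecorded, since the CRF and listings may hold them. It makes no claim about how many occurred or in which arm. It is an incomplete safety result that is cheap to repair, and it does not affect the validity of the primary comparison.

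**What to change.** In the SAP:

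- Add to 7.5 a table by arm of all-cause deaths and exacerbation-related deaths over the full 18 months.
- Add cause of withdrawal, with death as a named category, to the disposition table in 7.2, covering months 15 and 18 as well as the treatment period.

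In Protocol 9.1 and 9.2, reconcile the blanket exclusion with the SAE and SUSAR definitions. Exacerbations that are fatal, life-threatening or suspected to be caused by the product should be captured as safety events, and the exemption should stay for all other expected exacerbations. If conduct is already complete, apply the same classification retrospectively when the safety tables are built, and describe it in the report as a deviation from the protocol wording.

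The cost is a small number of additional SAE forms, or a retrospective review of existing records, and one or two extra tables.

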### Severity Assessment Definitions:

Mild: Transient symptoms that do not affect the subject's daily activities.

Moderate: Evident symptoms that have a moderate impact on the subject's daily activities.

Severe: Symptoms that have a considerable impact on the subject's daily activities.

All adverse events, both severe and non-severe, will be recorded in the corresponding section of the case report form.

### Causal Relationship with the Investigational Medicinal Product

Probable: There are sufficient reasons and documentation to assume the existence of a causal relationship.

Possible: A causal relationship is conceivable and cannot be ruled out.

Unlikely: The event is most likely related to an etiology other than the investigational medicinal product.

## 9.2. Methods and Schedule Used to Assess, Record, and Analyze the Safety Parameters

### Definitions:

- **Adverse Event (AE):** any untoward health occurrence in a Subject or a clinical trial subject treated with a medication and which does not necessarily have a causal relationship with the treatment. Exacerbations of COPD will not be considered Adverse Events because they constitute events that are to be expected within the course of the disease and their quantification is the primary objective of this trial.
- **Adverse Reaction (AR):** any unintended and harmful response to an investigational medicinal product, regardless of the dose administered.

- **Serious Adverse Event (SAE):**

Any adverse event that, at any dose:

- Leads to death.
- Is life-threatening for the subject (term “life-threatening” included in the definition of SAE refers to the fact that the Subject is at a risk of dying as a result of the event but not that, had the event been more intense, it could have caused the Subject's death).
- Results in the hospitalization or prolongation of an existing hospitalization.
- Causes a permanent or significant disability or incapacity.
- Results in a congenital anomaly or birth defect.
- Involves the transmission of any infectious agent (through the medicinal product).

The investigator shall rely on their own medical judgment to determine whether an Adverse Event is serious in other situations. Major medical events that, despite not posing an immediate risk of death or not resulting in death or hospitalization, may endanger the subject or require intervention to prevent one of the other outcomes listed in the above definition, should also be considered serious.

- **Suspected Unexpected Serious Adverse Reaction (SUSAR):** an adverse reaction whose nature or seriousness is not consistent with the product information (e.g., the investigator's brochure in the case of an investigational medicinal product not authorized for marketing or a summary of product characteristics in the case of an authorized medicinal product).

Adverse reactions can be classified into:

- **Local reactions**

Those appearing in the administration site. They may manifest as a mild burning, swelling, or itchy sensation in the oropharyngeal region. Gastrointestinal discomfort may develop in some cases. The onset of local reactions does not imply that the dosing schedule should be discontinued or changed. Their presence should be carefully assessed.

- **Systemic reactions**

Those appearing in parts of the body other than the administration site. The severity of these adverse reactions shall be scored according to the following grading system^149:

**Grade 1:** Transient, mild systemic reaction or mild discomfort (<48 hours) not requiring medical intervention nor therapy.

**Grade 2:** Moderate systemic reaction leading to a moderate limitation in the subject's activity and requiring barely any medical intervention or therapy.

**Grade 3:** Severe systemic reaction leading to a severe limitation in the subject's activity and requiring some sort of medical therapy/care, and, potentially, hospitalization.

**Grade 4:** Life-threatening reaction leading to an extreme limitation in the subject's activity and requiring medical therapy and intervention and, probably, hospitalization or palliative care.

Adverse events, broken down by severity and intensity, will be summarized using the MedDRA dictionary, by treatment group, system organ class, and preferred term, indicating the number of subjects per treatment group, the number and frequency of subjects reporting the event, and the number of events.

### **9.3. Procedures for Recording and Reporting Adverse Events and Intercurrent Diseases, and for Submitting their Reports**

All events meeting the definition of an adverse event should be collected and recorded between the start of the first trial-related activity (after the subject's signature of the informed consent) and the end of the post-treatment follow-up period required by the protocol. Subjects will be questioned whether they noticed any adverse event during each visit to the site. All adverse events, whether observed by the investigator or reported by a subject, should be recorded in the corresponding section of the case report form and evaluated by the investigator.

The minimum information to be specified shall be the description, severity, duration, temporal sequence, and method of detection of the adverse event. The treatment administered to manage the event must also be specified.

The investigator shall immediately report all serious adverse events and/or suspected unexpected serious adverse events (SUSARs), regardless of their relation to the investigational medicinal product, by telephone ( [REDACTED] ) or fax ( [REDACTED] ), to the staff of Inmunotek's Medical Department (always within the first 24 hours of their onset). The initial and follow-up reports shall identify the trial subjects by a unique identification code assigned to each one of them.

[name]  
Traductor-Intérprete Jurado de INGLÉS  
Nº 9971

The regulations in force will be followed when issuing the safety information notification to the Health Authorities, the Research Ethics Committees, and the investigators.

If a suspected unexpected serious adverse reaction occurs within the context of a double-blind clinical trial, the treatment code of the particular subject must be disclosed for reporting purposes. Whenever possible, blinding should be maintained for the investigator and the persons responsible for the analysis and interpretation of the results, as well as for drafting the study conclusions.

